13.8 Sample Size Calculations

13.8.1 Allocation

To encourage study participation, a 2:1:1 randomization will be used where at most half as many subjects will be assigned to the lurasidone and placebo arms as compared to the K/N study arm. The goal will be to have 62 subjects randomized to K/N and 31 subjects randomized to each of K/L and K/P for a total of 124 randomized subjects. The randomization takes place among Ketamine responders once confirmed by Medical Monitor.

13.8.2 Stage 1

The study goal is to achieve a total of 124 Ketamine responders for the Stage 2 evaluation. A total of 192 subjects are projected to be enrolled but this number may be reached sooner if the cumulative effect of the Ketamine response rate exceeding 70%, if the Stage 1 loss rate being less than 8% (15 subjects), or if the Stage 2 loss rate being less than 8% (9 subjects). Thus, there would be 177 subjects who complete Stage 1 before considering Ketamine response. The literature and prior experience suggests that 70% of those treated with ketamine will have an adequate reduction in depression and suicidality which equates to 124 Ketamine responders (177×0.7) who would be available for randomization. More subjects will need to be enrolled if the Ketamine response rate was lower than 70% or the randomization refusal rate was higher than 8%, considered to be part of Stage 2 losses.

13.8.3 Stage 2

Stage 2 will investigate the study hypotheses. The primary efficacy hypothesis is that K/N will delay the time to relapse relative to K/L and K/P. The goal will be to have 62 subjects randomized to K/N and 31 subjects randomized to K/L and K/P. These numbers are based on the Ketamine Responders. See **Error! Reference source not found.** for the total number of K/N and K/L subjects required to test the primary efficacy hypothesis. The sample size requirements are shown just for K/N and K/L. .

The study is powered based on the number of subjects randomized to K/N vs. K/L. In order to achieve 90% study power with two-sided 0.05 Type I error, a total of 56 K/N subjects, 28 K/L subjects, and 28 K/P subjects must be evaluated for time to relapse over the full 6 weeks. This is based on the assumption of a 30% relapse rate in the K/N treatment group and a 70% relapse rate in the K/L and K/P treatment groups. A larger gap in the relapse rate is expected based on the literature, so this is believed to be a conservative assumption. These calculations assume a loss of 8% during Stage 2.

Table 12 Time to Relapse: K/N and K/L Groups Followed for 6 Weeks

	90% Power	Reaching Significance
Test significance level, α	0.05	0.05
1 or 2 sided test?	2	2
K/L relapse-free % p_1 at Week 6	30%	30%
K/N relapse-free % p_2 at Week 6	52%	70%
Hazard ratio, $h=\ln(p_1) / \ln(p_2)$	1.841	3.376
Power (%)	90	N/A
Total N	112	112
Total N of relapses required, R	48	62
Total N accounting for 8% Stage 2 losses	124	124
Total N accounting for 30% K non-responders	177	177
Total N accounting for 8% Stage 1 losses	192	192

The secondary efficacy hypotheses will also be evaluated using a hierarchical testing strategy where testing to support labeling claims continues as long as two-sided $p=0.05$ is reached. The first such hypothesis to be tested for the depression endpoints is whether K/N separates from K/L and K/P by 72 hours, with sustained difference between groups thereafter (see **Error! Reference source not found.**). There will be 90% power and two-sided 5% Type I error to detect a 0.754 effect size for the comparison of the K/N against the K/L and K/P treatment groups.

Table 13 Two Group T-test: Equal Effect Sizes

	90% Power	Reaching Significance
Test significance level, α	0.05	$p=0.05$
1 or 2 sided test?	2	2
Effect size, $\delta = \mu_1 - \mu_2 / \sigma$	0.754	0.456
Power (%)	90	N/A
Total N	112	112

Next, all-cause discontinuation (including discontinuation for continued suicidal ideation) will be tested. The hypothesis is that the percent discontinued prior to Week 6 will be lower in K/N than K/L and K/P using a lifetable approach (see **Error! Reference source not found.**).

Table 14 Two Group Log Rank Test: Time to All-cause Discontinuation

	90% Power	Reaching Significance
Test significance level, α	0.05	0.05
1 or 2 sided test?	2	2
K/L success rate p_1 at Week 6	0.225	0.225
K/N success rate p_2 at Week 6	0.6	0.43
Hazard ratio, $h = \ln(p_1) / \ln(p_2)$	3.89	1.77
Power (%)	90	N/A
Total N	112	112
Total # discontinued required, D	60	72

The next hypothesis to be tested is whether K/N will separate from K/L and K/P starting at Day 7, with sustained difference thereafter (see **Error! Reference source not found.**).

The next hypothesis to be tested is whether improvements within the K/N group observed at Week 2 will remain stable to end of study (see **Error! Reference source not found.**).

Table 15 One Group t-test: No Mean Change

	1	2	3	4
Test significance level, α	0.050	0.050	0.050	0.050
1 or 2 sided test?	2	2	2	2
Effect size, $d = m_A - m_0 / s$	0.441	0.636	0.267	0.384
Power (%)	90	90	50	50
N	56	28	56	28

The last secondary hypothesis to be tested is whether C-SSRS scores will remain < baseline for 4 weeks following treatment discontinuation (i.e., “crisis” will resolve within the 6 week time period with most favorable outcomes in the K/N group as compared to K/L (see **Error! Reference source not found.**)).

Table 16 Fisher Exact Test: Normalized C-SSRS Score Percent Scenarios

	1	2	3	4
Test significance level, α	0.050	0.050	0.050	0.050
1 or 2 sided test?	2	2	2	2
Control Success %, p_1	30%	40%	50%	60%
K/N Success %, p_2	66.7%	76%	84%	91%
Odds ratio, $y=p_2(1-p_1)/[p_1(1-p_2)]$	4.674	4.750	5.250	6.741
Power (%)	90	90	90	90
n_1	28	28	28	28
n_2	56	56	56	56
Ratio: n_2 / n_1	2	2	2	2
Pairwise $N = n_1 + n_2$	84	84	84	84

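### Table 12 claims 90% power for 52% vs 30% relapse-free; the text assumes 70% vs 30%, and at the printed effect the powered comparison has only about 50–56% power

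*Combined protocol and SAP*

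**What the plan says.** Section 13.8.3 names the comparison that drives the sample size: "The study is powered based on the number of subjects randomized to K/N vs. K/L". It sets the target at 90% power with a two-sided 5% error rate. The numbers it gives for this target are "a total of 56 K/N subjects, 28 K/L subjects, and 28 K/P subjects must be evaluated for time to relapse", each with six weeks of follow-up. The effect behind this is stated next; the calculation is "based on the assumption of a 30% relapse rate in the K/N treatment group and a 70% relapse rate in the K/L and K/P" arms. In relapse-free terms that is 70% vs 30%.

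Table 12 has two columns, one for 90% power and one for just reaching significance (power shown as not applicable). K/L is 30% relapse-free in both. The row "K/N relapse-free % p_2 at Week 6" reads 52% in the first column and 70% in the second. The hazard ratios are 1.841 and 3.376, and the relapses required are 48 and 62. Total N is 112 in both.

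Tables 13 and 14 use the same two columns the other way round, with the larger effect under 90% power. For Table 13 the text says "There will be 90% power and two-sided 5% Type I error to detect a 0.754 effect size", and the just-significant effect is 0.456. In Table 14 the row "K/N success rate p_2 at Week 6" reads 0.6 for 90% power and 0.43 for significance, with hazard ratios of 3.89 and 1.77.

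**The concern.** The text and its table attach the same 90% power and the same subject numbers to two very different effects: a 40-point difference in the text and a 22-point difference in the table. Both cannot be right.

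This is the sample-size table for the primary endpoint. A reader who relies on it would think the trial very likely to detect a hazard ratio of 1.84. After a non-significant result, that reader could wrongly conclude that an effect of that size had been excluded with 90% power.

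**Working it through.** **Inputs** (Section 13.8.3 and Table 12): two-sided α = 0.05; 56 K/N and 28 K/L evaluable; K/L relapse-free 30%; K/N relapse-free 52% (table) or 70% (text); six weeks of follow-up.

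**1. Hazard ratios, by the table's formula ln(p1)/ln(p2).** ln(0.30)/ln(0.52) = 1.841 and ln(0.30)/ln(0.70) = 3.376. Both printed values are right for the rate above them, so each rate and hazard ratio sit together as a pair.

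**2. Power at the printed effect.** Expected relapses are 56 × 0.48 + 28 × 0.70 = 46.5. Schoenfeld power is Φ(ln HR × √(d·π(1−π)) − 1.96) with π = 2/3:

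- 52% vs 30%: ln 1.841 = 0.610; √(46.5 × 2/9) = 3.214; Φ(1.962 − 1.960) = **50%**.
- 70% vs 30%: d = 56 × 0.30 + 28 × 0.70 = 36.4; ln 3.376 = 1.217; √(36.4 × 2/9) = 2.844; Φ(3.460 − 1.960) = **93%**.

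**3. Other methods, 56 vs 28.** The simulation used exponential times censored at week 6 and 20,000 runs.

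| Method | 52% vs 30% | 70% vs 30% |
|---|---|---|
| Schoenfeld | 50% | 93% |
| Freedman | 56% | 96% |
| Simulated log-rank | 54% | 96% |
| Simulated Gehan | 52% | 95% |
| Two proportions | 48% | 95% |
| Fisher exact | 43% | 93% |

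**4. Other readings of a total N of 112 (Schoenfeld).**

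| Reading | Expected relapses at 52/30 | Power at 52/30 |
|---|---|---|
| 56 vs 28 | 46.5 | 50% |
| 112 split 2:1 | 62.0 | 62% |
| K/N vs both controls pooled, 56 vs 56 | 66.1 | 70% |

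The highest figure found, 83%, needs 62 vs 62 and a one-sided test. At a hazard ratio of 1.841, 90% power needs about 127 relapses with 2:1 allocation or 113 with 1:1. The table prints 48, and even 113 exceeds the 112 evaluable subjects.

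**5. Where the 52% comes from.** With 56 vs 28, the K/N rate at which the expected test statistic just equals 1.96 is 0.520 (hazard ratio 1.840). That is the entry printed under 90% power. It would be 0.488 for 112 split 2:1 and 0.472 for 56 vs 56, so the printed value fits only 56 vs 28. The same calculation for Table 14 gives 0.429, against 0.43 printed in its significance column. Table 13 also fits 56 vs 28: (1.960 + 1.282) × √(1/56 + 1/28) = 0.750, or 0.759 with the t distribution, against 0.754 printed.

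**6. Difference detectable with 90% power, 56 vs 28.** K/N relapse-free of about 67.5% (Schoenfeld), 65% (simulated log-rank) or 64% (Freedman) against 30%: a gap of 34 to 37.5 points.

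**7. The relapse counts.** In 112 subjects split 2:1, expected relapses are 48.5 at 70/30 and 62.0 at 52/30. The printed 48 and 62 match these under their present column headings. Table 14's 60 and 72 compare with 58.8 and 71.5. The counts therefore look like expected numbers in 112 subjects rather than required numbers in the 84 of the powered pair. This is an inference, since no formula is given and the match is not exact.

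**8. Table 14 hazard ratio.** ln(0.225)/ln(0.6) = 2.92, not 3.89. A value of 3.89 would need a K/N rate of 0.68. The neighbouring ln(0.225)/ln(0.43) = 1.77 is right.

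**The case against.** The strongest reply is that this is a misprint in a planning table. The assumption is stated properly in the prose just before it, power at that assumption exceeds 90%, and beating both comparators there still has joint log-rank power of about 93% by simulation. No test, analysis set or patient number changes. All of that stands: the trial is not undersized for the effect its text assumes, and the 50–56% applies only to the effect in the table.

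It does not remove the error. The table states a power for the primary endpoint that the design does not deliver at the printed effect, and nothing in the document corrects it.

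A second objection is that the transposition is inferred, because the document does not say whether text or table governs. That is fair. The inference rests on three facts that agree: the prose assumption, the 52% being the just-significant value for 56 vs 28, and the opposite column order in Tables 13 and 14.

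A third is that moving two rows leaves a count of 48 beside 70% vs 30%, where 84 subjects would yield about 36 relapses. This also stands, and is why the counts need restating in the same revision. The Table 14 hazard ratio is a separate, smaller error on a secondary endpoint.

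**Conclusion.** The concern holds. Table 12 contradicts the text of Section 13.8.3, and its 90% cannot be reproduced. For K/N vs K/L with 56 vs 28 evaluable, power at 52% vs 30% is about 50–56% by log-rank methods and lower (43–48%) for a comparison of proportions. At 70% vs 30% it is about 93–96%. The most plausible explanation is that the K/N rate and hazard ratio were exchanged between the columns.

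The figures assume proportional hazards, two-sided 5% and full six-week evaluation of 84 subjects; the simulations also assume exponential times. Sample size is unaffected if the text's assumption governs. If the sponsor did intend 52% vs 30%, it is not: about 127 relapses at an average relapse probability of (2 × 0.48 + 0.70)/3 = 0.553 means about 230 evaluable subjects in the two arms, against 84 planned.

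**What to change.** - **Table 12:** have the sponsor confirm that the text's assumption governs, then exchange only the K/N rate and hazard ratio between columns. The 90%-power column then shows 70% vs 30% and 3.376, with a note that computed power is about 93–96%. The significance column shows 52% vs 30% and 1.841, about 50% power by Schoenfeld.
- **Relapse and discontinuation counts (Tables 12 and 14):** do not move them with the other rows. Restate them for the 84-subject K/N plus K/L comparison, say whether they are required or expected counts, and name the formula. For orientation, required events for 90% power at 70/30 and at 60/22.5 are about 32 and 41 (Schoenfeld) or 27 and 34 (Freedman); expected events in 56 + 28 are about 36 and 44.
- **Table 14:** correct the hazard ratio from 3.89 to 2.92, once the sponsor confirms that 0.6 is the intended rate. Schoenfeld power at 0.6 with 56 vs 28 is 92%, which supports it.

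The cost is a few table cells and one named formula. The design, the tests and the 124 randomized stay as they are.

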Subjects who meet study criteria for relapse at any point during the study will be withdrawn from the study and offered clinically-appropriate treatment as determined by the treating study physician, which may

include inpatient hospitalization, repeated administration of ketamine, electroconvulsive therapy (ECT), or other treatments determined by professional judgment. Subjects who demonstrate therapeutic benefit from experimental drug NRX-101 (DCS+ lurasidone) at study completion may be offered prescribed DCS by their treating psychiatrist.

The Schedule of Study Activities (Table 3) summarizes the frequency and timing of efficacy, PK, and safety measurements applicable to this study. With the exception of post-dose assessments, visit-specific subject-reported outcomes assessments should be conducted or completed before any tests, procedures, or other consultations for that clinic visit to prevent influencing subject perceptions. A recommended order of study procedures will be provided to sites as a separate document.

Actual dates and times of assessments will be recorded in the source documentation and electronic Case Report Form (eCRF).

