13.9 Overall Type 1 Error Control

The overall Type I error is two-sided 5%. No interim analyses are planned.

A hierarchical testing plan is in place to control Type I error to extend labeling claims in the following pre-defined testing order where statistical significance (two-sided $p < 0.05$) is required at each step:

1. Primary: K/N will delay time to relapse relative to K/L and K/P
2. Secondary: K/N will separate from K/L and K/P by 72 hours, with sustained difference between groups thereafter

3. Secondary: All-cause discontinuation (including discontinuation for continued suicidal ideation) will be lower in K/N than K/L and K/P.
4. Secondary: K/N will separate from K/L and K/P starting at Day 7, with sustained difference thereafter
5. Secondary: Improvements within the K/N group observed at Week 2 will remain stable to end of study.

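### The 90% power at effect size 0.754 is for one pairwise comparison (joint power against both comparators is about 82%), and the power figures for claims running to Week 6 leave out the withdrawal of relapsers

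*Combined protocol and SAP*

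**What the plan says.** Section 13.8.3 introduces Table 13, for the claim of separation by 72 hours with a sustained difference afterwards, with the statement "There will be 90% power and two-sided 5% Type I error to detect a 0.754 effect size for the comparison of the K/N" group against K/L and K/P. The table gives a total N of 112. Earlier in the same section, "a total of 56 K/N subjects, 28 K/L subjects, and 28 K/P subjects must be evaluated", following from the allocation rule in 13.8.1 that "a 2:1:1 randomization will be used". On attrition it adds: "These calculations assume a loss of 8% during Stage 2".

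Section 13.4.2 words the first secondary hypothesis as separation from both comparators. Section 13.9 requires two-sided p<0.05 at each step and names both comparators at steps 2, 3 and 4; step 4, for example, reads "Secondary: K/N will separate from K/L and K/P starting at Day 7, with sustained difference thereafter". Step 5, powered in Table 15, has no comparator: it asks "whether improvements within the K/N group observed at Week 2 will remain stable to end of study".

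On relapse, 13.8.3 says of its calculation: "This is based on the assumption of a 30% relapse rate in the K/N treatment group and a 70% relapse rate in the K/L" arm, with the same 70% for K/P. Section 8.1 says: "Subjects who meet study criteria for relapse at any point during the study will be withdrawn from the study". Section 6.2 ends efficacy data collection at six weeks or at earlier rescue. Section 13.10.4 makes MMRM in the ITT population the primary analysis of the secondary endpoints.

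**The concern.** Two things do not fit together.

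First, a power attached to a claim against two comparators should be the probability of succeeding against both. If 0.754 was derived for one comparison, the stated 90% is too high for the claim. Step 2 is the first secondary gate, so its power also limits how often steps 3 to 5 are reached.

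Second, several claims extend to Week 6 or beyond, yet their power rests on 56 and 28 subjects. If relapsers leave, and the plan expects 30% and 70% to relapse, those denominators do not exist at Week 6. A reader relying on 13.8.3 would then overestimate how well the sustained part of the claims can be shown, and how much a no-change result in Table 15 says about stability.

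**Working it through.** **Inputs.** Evaluable 56/28/28, two-sided 0.05, effect size 0.754, relapse 30% (K/N) and 70% (K/L, K/P), all from 13.8.3; withdrawal at relapse from 8.1; both comparators from 13.4.2 and 13.9.

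**1. Reproduce Table 13.** Noncentrality = 0.754 × √(56 × 28 / 84) = 3.26 on 82 degrees of freedom; power 89.6% (normal approximation 90.3%). Pooling the comparators, 56 against 56, gives 97.7%. So 0.754 is the pairwise 56 against 28 figure, although the table row reads 112.

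**2. Joint power.** The two test statistics share the K/N arm. Their correlation is (1/56) / (1/56 + 1/28) = 1/3. The bivariate normal probability that both are significant is 81.7% starting from 89.6%, or 82.3% starting from 90%. Simulated t-tests (200,000 runs) give 81.8%. For 90% joint power each comparison needs about 94.6%, which is an effect size of about 0.835 at 56/28/28.

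**3. The same point in the other tables.**
- Table 14 (0.60 against 0.225 still in the study): expected pairwise discontinuations 56 × 0.40 + 28 × 0.775 = 44.1. Hazard ratio ln 0.225 / ln 0.60 = 2.92 (the table prints 3.89, which does not follow from its own rates). Power = Φ(√(44.1 × 1/3 × 2/3) × ln 2.92 − 1.96) = 91.8% for one comparator, about 85% for both.
- Table 16: exact Fisher power 87% to 89% for one comparator, about 78% to 81% for both, if both are required. Section 13.8.3 describes this hypothesis against K/L only, 13.4.2 against both, and 13.9 does not list it.
- Table 15 is K/N only, so the point does not arise.

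**4. Numbers still rated at Week 6.** K/N: 56 × 0.70 = 39.2. Each comparator: 28 × 0.30 = 8.4. Relapse withdrawals: 16.8 + 19.6 + 19.6 = 56 of the 112. The 8% allowance is already used in going from 124 to 112, so it cannot cover these. Early visits are little affected: if the relapse hazard is constant (an assumption), about 55 against 26 remain at 72 hours and 53 against 23 at Day 7.

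**5. Table 13 effect size at Week 6, observed cases only.** Noncentrality = 0.754 × √(39 × 8 / 47) = 1.94 on 45 degrees of freedom; power 47.7% for one comparator. Simulation gives 26% for both. For 90% against one comparator the effect size would have to be 1.29.

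**6. Under MMRM.** Power depends on the within-subject correlation, which the documents do not give. As an illustration: visits Day 7 to Day 42, constant relapse hazard, data missing at random, effect size 0.754.

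| Assumed correlation between visits | One comparator | Both |
|---|---|---|
| AR(1), 0.3 to 0.9 | 52% to 68% | 29% to 50% |
| Compound symmetry, 0.3 to 0.9 | 55% to 80% | 34% to 66% |

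**7. Table 15, column 1.** One-sample t-test, effect size 0.441: noncentrality 0.441 × √56 = 3.30, power 90.0% (reproduces). With n = 39: 0.441 × √39 = 2.75, power 76.5%. The effect size detectable with 90% power rises to 0.53.

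**8. Table 16 with 39 against 8 observed:** 44% to 47% for one comparator.

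**The case against.** The strongest reply is that the planned analysis is not a t-test on those remaining. MMRM uses every rating before withdrawal, so 48% and 26% are not the power of the specified analysis. That stands: they are lower figures, and step 6 shows how far the answer moves with the correlation. Even so, none of the illustrated values reaches 90%. All these figures also hold the effect size at 0.754 at Week 6, although removing relapsers may change the contrast.

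The pairwise basis is partly disclosed. Section 13.8.3 says that the study is powered on K/N against K/L, and Table 16 labels its N as pairwise. What remains is that the Table 13 sentence attaches a pairwise figure to a two-comparator claim.

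The sentence also introduces a 72-hour claim, when few subjects would have left. That is right: attrition bears only on the later part of the claim, and the plan does not say that a significant Week 6 test alone is required. Table 14 is untouched by attrition, because leaving is its event. For Table 16, the 56 and 28 would survive if withdrawn relapsers counted as failures, but the plan does not say so.

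A reader might infer that the secondary powers assume nobody leaves. They do not: 112 is already net of the planned loss. Nor does a smaller n make the step 5 claim less likely to be reached. Table 15 tests for a change, so fewer subjects make a true change easier to miss.

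**Conclusion.** The point holds in two separate parts.

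**Joint power.** With complete data, the design gives about 82%, not 90%, for beating both comparators at 0.754. This needs no outside assumption beyond equal effects against the two comparators. It applies to Tables 13 and 14, and to Table 16 if both comparators are required.

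**Attrition.** Under the plan's own relapse rates and its withdrawal rule, about 39 K/N subjects and 8 per comparator are still rated at Week 6. This bears on the sustained part of the Table 13 claim and on Tables 15 and 16. Week 6 power for Table 13 is at least about 48% (one comparator) or 26% (both) and below the full-data values of 90% and 82%; the documents do not allow a single figure. For Table 15, power to detect a change of 0.441 is 77%, so a no-change result is weaker evidence of stability than stated.

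A reader might extend this to the primary endpoint. The documents do not support that from this point: at the 30% and 70% relapse rates in the text, simulated joint log-rank power is about 93%. That is conditional on those rates; the 90% column of Table 12 uses 52% against 30% relapse-free, which is a separate matter.

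**What to change.** In 13.8.3:

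1. Label 0.754 as the pairwise 56 against 28 effect size and state about 82% joint power, or give 0.835 as the effect size for 90% joint power. State joint power for Table 14 as well, and say whether the Table 16 hypothesis requires one comparator or both.
2. Add the expected number still rated at each visit, by arm, under the assumed relapse rates.
3. Restate Week 6 power for the Table 13 claim as a range under the planned MMRM, with the correlation and missing-data assumptions written out.
4. Restate Tables 15 and 16 on the expected numbers, and for Table 16 say how withdrawn relapsers are counted.

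The cost is revised text and tables in one section. No change to sample size or study conduct is needed; in particular, the point does not depend on changing how relapsers are followed.

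### Table 16 gives 90% power for a two-sided Fisher exact test in four scenarios; at 28 versus 56 that test has 87.9%, 87.2%, 87.4% and 89.1%.

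*Combined protocol and SAP*

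**What the plan says.** Section 13.8.3 (Stage 2) closes with a table of detectable differences for the last secondary hypothesis, on C-SSRS scores in the four weeks after treatment stops. Table 16 is titled "Fisher Exact Test: Normalized C-SSRS Score Percent Scenarios". Its rows give:

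- alpha of 0.050 in each column, and a two-sided test in each ("1 or 2 sided test? 2 2 2 2");
- control success of 30%, 40%, 50% and 60%;
- K/N success: "K/N Success %, p_2 66.7% 76% 84% 91"%;
- odds ratios of 4.674, 4.750, 5.250 and 6.741;
- 28 control and 56 K/N subjects, 84 in each pairwise comparison;
- power: "Power (%) 90 90 90 90".

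The group sizes are the evaluable numbers given earlier in the same section, where "a total of 56 K/N subjects, 28 K/L subjects, and 28 K/P subjects must be evaluated" over the six weeks. They are what is left of 62, 31 and 31 randomized after the assumed 8% Stage 2 loss.

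**The concern.** Fisher's exact test is conservative at group sizes of 28 and 56: its attained type I error is below the nominal 5%, and it gives up power compared with an uncorrected chi-square test. A table that names Fisher's test should show the power of that test. Table 16 contains every input needed to check this, and the figure of exactly 90% in all four columns looked more like the result of a large-sample formula.

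At stake is whether the plan's stated power for this comparison is right. A reader would take it that the named test detects the listed differences with 90% power at the listed sample sizes.

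**Working it through.** **Inputs, all from Table 16.** n1 = 28 (control), n2 = 56 (K/N), two-sided alpha 0.05, and (p1, p2) = (0.30, 0.667), (0.40, 0.76), (0.50, 0.84), (0.60, 0.91).

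**Step 1: check the rates through the table's own odds ratios.** OR = p2(1 − p1) / [p1(1 − p2)].

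- 0.667 × 0.70 / (0.30 × 0.333) = 4.674
- 0.76 × 0.60 / (0.40 × 0.24) = 4.750
- 0.84 × 0.50 / (0.50 × 0.16) = 5.250
- 0.91 × 0.40 / (0.60 × 0.09) = 6.741

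All four agree with the table, so the printed rates are the ones that were used.

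**Step 2: reproduce the stated 90%.** The pooled normal approximation without continuity correction is

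power = Φ{ [ (p2 − p1) − 1.96·s0 ] / s1 }, with s0² = p̄(1 − p̄)(1/n1 + 1/n2), s1² = p1(1 − p1)/n1 + p2(1 − p2)/n2, and p̄ = (n1p1 + n2p2)/(n1 + n2).

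Scenario 1: p̄ = (8.4 + 37.352)/84 = 0.5447, s0 = 0.1153, s1 = 0.1071. Then (0.367 − 1.96 × 0.1153)/0.1071 = 1.318 (unrounded inputs), and Φ(1.318) = 0.906. The other three scenarios give 0.905, 0.902 and 0.904. Solving the same formula for 90% power at 2:1 allocation returns 28 controls in all four columns. The 90% row is therefore consistent with this approximation.

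**Step 3: power of the named test.** Exact power is

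Σ over x = 0…28, y = 0…56 of Bin(x; 28, p1) · Bin(y; 56, p2) · 1[two-sided Fisher p(x, y) ≤ 0.05],

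where the two-sided p-value sums the tables no more probable than the one observed. All 29 × 57 outcomes were enumerated.

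| Scenario | p1 | p2 | Stated | Normal approx. | Fisher exact | Shortfall (points) |
|---|---|---|---|---|---|---|
| 1 | 30% | 66.7% | 90% | 90.6% | 87.9% | 2.1 |
| 2 | 40% | 76% | 90% | 90.5% | 87.2% | 2.8 |
| 3 | 50% | 84% | 90% | 90.2% | 87.4% | 2.6 |
| 4 | 60% | 91% | 90% | 90.4% | 89.1% | 0.9 |

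**Step 4: other readings of the test.** Fisher's test with the doubled one-tail p-value gives less power: 84.7%, 85.6%, 85.7% and 86.1%. The mid-p version gives 90.8%, 89.9%, 89.5% and 89.6%, but it is not the test named. One-sided Fisher at 0.05 gives 91.3% to 91.9%, but the table says two-sided.

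**Step 5: rates that would give 90%.** Keeping 28 versus 56 and the same control rates, two-sided Fisher first reaches 90% at K/N success of about 68.0%, 77.4%, 85.2% and 91.4%. On a half-point grid the smallest adequate values are 68%, 77.5%, 85.5% and 91.5%, with power of 90.2%, 90.2%, 90.8% and 90.4%.

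**The case against.** There are three fair objections.

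- **Rounding.** K/N success is printed to the whole percent in columns 2 to 4. If the true value in column 4 were 91.5%, Fisher power would be 90.4% and that column would be right. This does not stand: 91.5% would give an odds ratio of 0.915 × 0.40 / (0.60 × 0.085) = 7.18, and the table prints 6.741. Columns 1 to 3 miss 90% even at the top of their rounding range (88.0%, 88.3% and 88.6%).
- **Sample size.** The trial randomizes 31 and 62 to this comparison. At those numbers Fisher power is 92.6%, 91.7%, 91.3% and 92.3%, and at 30 versus 60 it is already 91.3%, 90.3%, 90.1% and 91.4%. This limits the practical effect, since losses somewhat lower than planned would restore 90%. It does not correct the table, which ties its power to 28 and 56.
- **Importance.** Table 16 serves the last secondary hypothesis only. That hypothesis does not appear among the five ordered steps in Section 13.9, the sample size rests on time to relapse, and the control rates are round illustrative values. A gap of one to three points is small beside the uncertainty in those values. All of this stands, and it is why the point is minor.

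**Conclusion.** The concern holds. At the sample sizes and success rates that Table 16 prints, a two-sided Fisher exact test at 0.05 has power of 87.9%, 87.2%, 87.4% and 89.1%, not 90%. Every column errs in the favourable direction, three of them by more than 2 points. The inputs are coherent with one another. The likely explanation, inferred because the figures match, is that power from an uncorrected normal approximation was placed under a Fisher exact heading.

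The result assumes independent binomial outcomes in the two groups and the usual definition of the two-sided Fisher p-value; the doubled-tail definition makes the shortfall larger. No sample size, primary analysis or listed step of the testing order is affected.

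**What to change.** Correct Table 16 in one of two ways:

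1. Keep the rates and restate the power row as 88%, 87%, 87% and 89%.
2. Keep 90% and restate the detectable K/N success rates as about 68%, 77.5%, 85.5% and 91.5%. The odds ratio row then becomes 4.958, 5.167, 5.897 and 7.176 (for example, 0.68 × 0.70 / (0.30 × 0.32) = 4.958).

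If an uncorrected chi-square test was intended for this comparison, the heading should name it in place of Fisher's test.

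The cost is an edit to one table. The figures become slightly less favourable, and nothing changes in the number of subjects or the conduct of the trial.
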